#### RANDOMIZATION

Patients will be randomized to receive M2A Magnum (trial group), or M2A Taper (control group). Patients have an equal opportunity of being assigned to the trial group or control group. Specifically:

In case of unilateral patients, the affected side of hip will be randomized to one of two groups. In case of bilateral patients, both sides of hip will be randomized to the same device (M2A Taper or M2A Magnum).

The randomization will occur via a random number generator (manual or computer). Block randomization will be used. Blocks of K patients will be created where K = 4. The possible sequences are AABB, BBAA, ABAB and BABA. Two sets of randomization blocks will be followed by unilateral and bilateral patients respectively. For unilateral patients, A or B represents the device assigned to affected side of the hip. For bilateral patients, A or B represents the device assigned to both affected sides of the hip.

The doctor or other health care professional does not choose the participants for each group. For Patients satisfying inclusion criteria, randomization will occur by retrieving the next randomly generated group assignment.

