## **PARTICIPANT POPULATION (SAMPLE SIZE)**

Participant population is determined based on primary/secondary endpoints of each subgroup following superiority or non-inferiority methodologies. Minimum sample sizes are determined in order to prove the hypotheses.

Primary Endpoint Accumulative Dislocation Rate at 5 year postoperative Superiority test – time to event

Null Hypothesis: $H_0$  $p_t = p_c$ Alternative Hypothesis: $H_a$  $p_t = p_c + d$ 

 $p_t$  = accumulative dislocation rate (1.8%)[2] in the trial group (Magnum) at 5 year postoperative.

 $p_c$  = accumulative dislocation rate (6.5%)[2] in the control group (M2A Taper) at 5 year postoperative.

α = 0.025 Significance Level (97.5% confidence)

β = 0.20 80% Power

 $Z_{1-a/2} = 2.24$  $Z_{1-\beta} = 0.84$ 

N = 150 per group.

Due to nature of this endpoint (occurrence of dislocation), it is not expected there will be significant lost to follow-up and patients usually come back to their operating surgeons for complications if any.

Primary Endpoint Range of Motion at 1 year postoperative Superiority test

Null Hypothesis:	H 0	$\mu_t = \mu_c$				
Alternative Hypothes	is: H a	$\mu_t = \mu_c + d$				
$\mu_t$ : mean of ROM in the trial group at 1 year postoperative.						
$\mu_c$ : mean of ROM in the control group at 1 year postoperative.						
α = 0.025	Significance	Level (97.5% confidence)				
β = 0.20	80% Power					
$Z_{1-a/2} = 2.24$ $Z_{1-\beta} = 0.84$						
d = 3.3 (degrees)	Clinically Rel	evant Difference in ROM based on literature.				
ξ = 7.1	Estimate sta This value is literature	ndard deviation of ROM at 1 year postoperative. based on results (preop and 1 year postop) from				

N = 95 (including 7.5% lost to follow-up) per group

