## INSTITUTIONS

there will be 5 sites recruiting 150 Magnum cases and 150 M2A Taper cases.

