## PARTICIPANT DATA MANAGEMENT

	PRE	OP	IMMEDIATE	3	6	1	2	3	4	5	7	10
	- O P	•	POST-OP	MO	MO	YR	YR	YR	YR	YR	YR	YR
Informed	x						X *					
Consent	~						~					
Demographic												
and Historical	Х											
Record												
Operative		v										
Record		^										
Metal ion												
concentrations	v			v	v	v	v	v	v	v	v	v
in blood and	^			^	^	^	^	^	^	^	^	^
urine												
Renal function												
(Creatinine	X			Х	X	Χ	Х	Χ	Χ	Х	Х	Χ
Clearance Test)												
Harris Hip Score	×			v	v	×	×			×		v
(Including ROM)	^			^	^	^	^			^		^
Postoperative				Y	Y	Y	Y			Y		Y
Thigh Pain				^	^	^	^			^		^
EQ5D	X			X	X	Χ	Χ	Χ	Χ	Χ	Χ	Χ
UCLA Activity	Y			Y	Y	Y	Y	Y	Y	Y	Y	Y
Score	^			^	^	^	^	^	^	^	^	^
Radiographic	x		x	x	x	x	x	x	x	x	x	x
Assessment	^		~	^	^	^	^	~	^	^	^	^
MRI										Y		
Assessment												
Additional	As needed											
Image	(for symptomatic patients only: having pain/discomfort on hip, higher ion											
Assessment	concentration than 7ppb or suspect of ARMD etc)											
(MRI / CT)	RI / CT)											
Complications &		Anytime										
Revisions												

The following table summarizes data collection required during the course of the study.

\* Informed consent will be obtained at the time of 2 year follow-up to continue to participation of the study.

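### Randomization prints a fixed block-of-4 rule with only four of the six balanced sequences, so the first two assignments in a block fix the last two; depending on list structure, 0% to 50% of assignments can be foreseen with certainty

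*Combined protocol and SAP*

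**What the plan says.** The Randomization section assigns patients 1:1 to M2A Magnum or M2A Taper in blocks of 4. On the content of the blocks it states: "The possible sequences are AABB, BBAA, ABAB and BABA". On the lists: "Two sets of randomization blocks will be followed by unilateral and bilateral patients respectively". On generation: "The randomization will occur via a random number generator (manual or computer"). On release, for patients who meet the inclusion criteria, "randomization will occur by retrieving the next randomly generated group assignment". It adds: "The doctor or other health care professional does not choose the participants for each group".

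The section does not say who holds the list, whether it is per site or shared, or how the next entry is kept from view. Institutions says that "there will be 5 sites recruiting 150 Magnum cases and 150 M2A Taper cases".

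Three other places bear on the point:
- Monitoring Plan includes the study protocol in the information given to investigators.
- Confidentiality restricts each doctor's view of the study database to that doctor's own patients.
- Patient Selection requires signed consent for enrolment where regulations call for it.

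No blinding is described anywhere.

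**The concern.** Six sequences of length 4 contain two As and two Bs. The plan uses four of them and gives no reason for omitting ABBA and BAAB. The omission makes the second half of every block a fixed function of the first half, and the rule is printed in a document that sites hold.

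An investigator who can foresee the device could delay or decline a patient whose hip looks stiff or prone to dislocate. Both primary endpoints of the randomised comparison, range of motion (ROM) at 1 year and dislocation at 5 years, depend on features that a surgeon can partly judge before enrolment. Preoperative ROM is collected (the Harris Hip Score row of the data table is marked "Including ROM"), so adjustment could remove the measured part of any imbalance in ROM.

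For dislocation there is less room to adjust. The control rate is given as "accumulative dislocation rate (6.5%)[2] in the control group (M2A Taper) at 5 year postoperative" and the Magnum rate as 1.8%. With 150 per group this implies 150 × 0.018 + 150 × 0.065 = 2.7 + 9.75 = 12.45 expected events.

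**Working it through.** The plan states no predictability figure, so there is none to reproduce.

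**Inputs.** Block size, sequences and strata come from Randomization; the 5 sites and 150 + 150 cases come from Institutions. Assumed: the listed sequences are equally likely, sites are of equal size, and foresight comes only from past assignments. Let q be the share of earlier assignments on the list that the observer has seen.

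**Structure of the listed sequences.**

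| Sequence | Positions 2, 3 | Positions 1, 4 |
|---|---|---|
| AABB | A, B | A, B |
| BBAA | B, A | B, A |
| ABAB | B, A | A, B |
| BABA | A, B | B, A |

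Both pairs are always opposite. Given position 1 alone, position 2 is an even chance.

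**Block position known.** Positions 1 and 2 are never certain. Position 3 is certain if position 2 was seen, and position 4 is certain if position 1 was seen. Otherwise the chance is even.
- Certain: (0 + 0 + q + q)/4 = q/2.
- Best guess correct: 0.5 + q/4.

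The six-sequence columns come from enumerating all six balanced sequences in the same way.

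| Observer | q | Certain, four | Best guess, four | Certain, six | Best guess, six |
|---|---|---|---|---|---|
| Sees every earlier assignment on the list | 1 | 50% | 75% | 33.3% | 70.8% |
| One of two equal surgeons on a per-site list, own patients only | 1/2 | 25% | 62.5% | 8.3% | 59.9% |
| One of five equal sites on a shared list, own patients only | 1/5 | 10% | 55% | 1.3% | 54.4% |

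The 50% does not depend on how the four sequences are weighted. If every past assignment is seen but the starting position is not known, simulation still gives 44% certain over 60 patients and 49% over 300, because the pattern reveals the position.

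**Shared list, block position unknown (q = 1/5).** The observer guesses the opposite of their own last patient, without knowing how many patients lie between. With four sequences, P(opposite) is 0.625 at gap 1, 0.5 at gap 2, 0.625 at gap 3 and 0.5 beyond. Gaps 1 and 3 have probabilities 0.2 and 0.2 × 0.8² = 0.128. Success is 0.5 + 0.125 × (0.2 + 0.128) = 54.1%, with 0% certain. With six sequences P(opposite) is 0.625, 0.583 and 0.542 at gaps 1 to 3, which gives 54.4%.

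**In patients.** 10% of 300 is 30. At 50%, a list of length n has 2·floor(n/4) + max(0, n mod 4 − 2) determined assignments. For 300 patients over 10 lists (5 sites × 2 strata) that is 140 to 150, as a maximum. The counts are lower if a case means a hip, because blocks are made of patients.

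**Proposed blocks of 4, 6 and 8.** All balanced sequences are used, sizes are equally likely, and the observer knows the set of sizes and sees every assignment. Simulation of 300 lists of 300 gives about 2% certain and 68% best guess. On a shared list with position unknown, the gap calculation gives 53.8%, against 54.1% now.

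**The case against.** The strongest reply is that the 50% figure needs conditions that the documents do not supply. It requires a per-site list with one surgeon, or colleagues who share assignments, or sight of the whole list. The wording about two sets of blocks fits one list per stratum, shared by all sites, at least as well, and doctors see only their own patients in the database. On that reading certainty is 0% to 10% and the best guess is 54% to 55%. With block position unknown, the omitted sequences do not matter: all six are marginally more guessable.

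The consequence would then be small. As an illustration with an assumed effect, suppose that acting on every best guess shifts enrolled patients' ROM by ±0.1 to 0.2 SD. With the plan's SD of 7.1 that is 0.71 to 1.42 degrees. The group difference moves by 2 × (2p − 1) × shift, where p is best-guess success: 0.12 to 0.23 degrees at 54.1%, 0.14 to 0.28 at 55%, and 0.71 to 1.42 at 75%. The plan's relevant difference is 3.3 degrees.

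This reply stands for the shared-list readings. It does not settle the matter, because the text does not exclude per-site lists. The database restriction also concerns study data, not the randomisation list.

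Two stronger inferences should be resisted. A reader might infer that half of all assignments were foreseeable in practice; nothing in the documents shows that the conditions for this were met. A reader might also infer that allocation was unconcealed. The plan does not describe concealment, but an undescribed procedure is not proof that none exists. The plan does tie randomisation to eligibility and says that clinicians do not choose who enters which group. That last statement is a principle, though, and it gives no mechanism against foreknowledge.

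**Conclusion.** The concern holds for the block rule as written and disclosed. The rule makes the last two assignments of every block a function of the first two, and investigators hold the key. The proportion foreseeable with certainty is 50% at most (75% best guess). It is 25% (62.5%) for two equal surgeons on a per-site list, 10% (55%) on a shared list with known block position, and 0% (about 54%) on a shared list with unknown position. These figures assume equal sites or surgeons and foresight from past assignments only; the best-guess values also assume equally likely sequences.

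The documents do not say which case applies. No bias is demonstrated, and its size cannot be derived from them. This is an avoidable design weakness that should be corrected because correction is cheap. It does not show that the randomised comparison is compromised.

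**What to change.** For patients not yet randomised:

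1. In Randomization, replace the fixed four-sequence rule with computer-generated permuted blocks drawn from all balanced sequences, with randomly varying sizes (for example 4, 6 and 8), within the unilateral and bilateral strata.
2. Keep block sizes and sequences in a restricted document and remove them from the protocol that sites hold. This must go with a new list, since investigators already have the printed sequences.
3. As a supporting wording change, state that the list is held outside the sites, whether it is shared or per site, and that each assignment is released only after consent and eligibility are recorded. The plan already requires eligibility, and consent where regulations require it; what is missing is recording before release, and custody of the list.

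The benefit is mainly against certainty. For an observer of the whole list the best guess remains at about 68%, which is why items 2 and 3 matter as well.

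The cost is a short text change, a restricted document, a new list and slightly looser balance between groups at any moment. The database is described only as data capture, so a release route may have to be set up. The change does nothing for patients already randomised; for them, preoperative ROM is available to compare the groups and to adjust.

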## INSTITUTIONS

there will be 5 sites recruiting 150 Magnum cases and 150 M2A Taper cases.

## PARTICIPANT DATA MANAGEMENT

	PRE	OP	IMMEDIATE	3	6	1	2	3	4	5	7	10
	- O P	•	POST-OP	MO	MO	YR	YR	YR	YR	YR	YR	YR
Informed	x						X *					
Consent	~						~					
Demographic												
and Historical	Х											
Record												
Operative		v										
Record		^										
Metal ion												
concentrations	v			v	v	v	v	v	v	v	v	v
in blood and	^			^	^	^	^	^	^	^	^	^
urine												
Renal function												
(Creatinine	X			Х	X	Χ	Х	Χ	Χ	Х	Х	Χ
Clearance Test)												
Harris Hip Score	×			v	v	×	×			×		v
(Including ROM)	^			^	^	^	^			^		^
Postoperative				Y	Y	Y	Y			Y		Y
Thigh Pain				^	^	^	^			^		^
EQ5D	X			X	X	Χ	Χ	Χ	Χ	Χ	Χ	Χ
UCLA Activity	Y			Y	Y	Y	Y	Y	Y	Y	Y	Y
Score	^			^	^	^	^	^	^	^	^	^
Radiographic	x		x	x	x	x	x	x	x	x	x	x
Assessment	^		~	^	^	^	^	~	^	^	^	^
MRI										Y		
Assessment												
Additional	As needed											
Image	(for symptomatic patients only: having pain/discomfort on hip, higher ion											
Assessment	concentration than 7ppb or suspect of ARMD etc)											
(MRI / CT)	RI / CT)											
Complications &		Anytime										
Revisions												

The following table summarizes data collection required during the course of the study.

\* Informed consent will be obtained at the time of 2 year follow-up to continue to participation of the study.

#### **METAL ION ANALYSIS**

Blood (serum) and urine will be collected at predetermined follow-up periods (3m, 6m, 1y, 2yr, 3y, 4y, 5y, 7 yr and 10y) to measure metal ion levels released (Co and Cr) from the articulating surfaces of M2A Magnum or M2A Taper cases. To create a baseline, blood (serum) and urine samples will also be taken preoperatively.

All patients agree to the invasive procedure of giving blood and will provide blood and urine samples for measurement of metal ions pre-operatively. Patients with an existing metal implant or fixation device will be excluded. The analysis of metal ion concentrations within both blood and urine will be conducted. Blood and urine sample collection and metal ion analysis follow the protocol included in the Appendix I.

Metal ion analysis will be conducted separately for unilateral and bilateral patients.

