## STUDY OBJECTIVE

The primary objectives of this clinical study include:

- Evaluate clinical efficacy and performance of M2A Magnum in Asian population in comparison to competitors' similar products.
- Investigate potential advantages of M2A Magnum compared to M2A Taper (28mm and 32mm) in terms of Range of Motion, Dislocation while maintaining the same function improvement and pain reduction.
- Investigate Metal-ion release and renal function in M2A Total Hip Arthroplasty.

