#### **ENDPOINTS**

	SUBGROUP 1	SUBGROUP 2			
PRIMARY ENDPOINTS*	Survivorship at 2 year postop	Dislocation (5 year postop), Range of			
		Motion at 1 year postop.			
SECONDARY	At all follow-up visits:	At all follow-up visits:			
ENDPOINTS	Survivorship up to 10 year	Survivorship up to 10 year (for			
	Harris Hip Score	Magnum arm)			
	Radiographic Assessment	Harris Hip Score.			
	Patient Satisfaction – EQ5D	Radiographic Assessment			
	UCLA	Patient Satisfaction – EQ5D			
	Complications including revisions	UCLA			
		Complications including revisions			
		Metal Ion release			
		MRI assessment to all available			
		patients at 5 year follow-up.			
		ADDITIONAL IMAGE ASSESSMENT FOR			
		SYMPTOMATIC PATIENTS			

\*For sample size calculations.

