#### **RENAL FUNCTION ANALYSIS**

Creatinine and creatinine clearance tests measure the level of the waste product creatinine in your blood and urine. These tests tell how well your kidneys are working. The substance creatine is formed when food is changed into energy through a process called metabolism. Creatine is broken down into another substance called creatinine, which is taken out of your blood by the kidneys and then passed out of your body in urine. See a picture of the kidneys.

Creatinine is made at a steady rate and is not affected by diet or by normal physical activities. If your kidneys are damaged and cannot work normally, the amount of creatinine in your urine goes down while its level in your blood goes up.

A creatinine clearance test measures how well creatinine is removed from your blood by your kidneys. A creatinine clearance test gives better information than a blood creatinine test on how well your kidneys are working. A creatinine clearance test is done on both a blood sample and on a sample of urine. eGFR /Creatinine clearance will be calculated, analyzed as described in Guideline for Chronic Kidney Disease (published by Japanese Society for Nephrology).[7] Renal function analysis will follow the protocol in Appendix I. All patients entered into the study agree to the invasive procedure of giving blood and urine samples for measurement of creatinine at preoperative and various postoperative visits.

Renal function will be conducted separately for unilateral and bilateral patients.

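### Metal-ion and renal results are analysed only separately by laterality, so no estimate uses all randomised patients; a laterality-stratified Magnum–Taper estimate should be added

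*Combined protocol and SAP*

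**What the plan says.** All references are to the combined protocol and SAP.

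- METAL ION ANALYSIS: "Metal ion analysis will be conducted separately for unilateral and bilateral patients".
- RENAL FUNCTION ANALYSIS: "Renal function will be conducted separately for unilateral and bilateral patients".
- RANDOMIZATION: "Two sets of randomization blocks will be followed by unilateral and bilateral patients respectively". Allocation is equal ("Patients have an equal opportunity of being assigned to the trial group or control group"), and a bilateral patient receives the same device in both hips.
- STUDY OBJECTIVE: one of the three primary objectives is "Investigate Metal-ion release and renal function in M2A Total Hip Arthroplasty".
- Hypotheses: in the subgroup table, Subgroup 2 is the randomised comparison. Its stated aim includes comparing ion release between the two devices, and renal function is among its endpoints. None of the three numbered hypotheses concerns ions or kidneys.
- ENDPOINTS: "Metal Ion release" is a secondary endpoint of Subgroup 2. Renal function does not appear in that table.
- PARTICIPANT POPULATION (SAMPLE SIZE): calculations are given for dislocation and range of motion only.
- INSTITUTIONS: "there will be 5 sites recruiting 150 Magnum cases and 150 M2A Taper cases".

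Nowhere is a combined or stratified Magnum–Taper estimate for ions or renal function described.

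**The concern.** The plan asks a between-device question about ion release in a randomised comparison, but its only analysis rule splits the patients into two groups and stops there. The reader will get two answers, each based on part of the sample, with no statement of how they combine or what to conclude if they differ.

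The bilateral result is the more exposed. If bilateral patients are few, that analysis could miss a substantial device difference, and a null result could be read as reassurance about the patients who carry two metal bearings. If the two results are combined only after both have been seen, the scale and the weights become data-driven choices.

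For renal function the reason to split is weaker. Ion load plausibly rises with the number of bearings. It is less obvious that a device effect on creatinine clearance would do so.

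**Working it through.** **No figure to reproduce.** The document gives no power, target difference, standard deviation or significance level for ion or renal results, and no expected bilateral share.

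**Inputs.** From the document: 150 per arm, equal allocation, separate randomisation blocks by laterality. Assumed: two-sided 0.05, a common standard deviation σ, a "case" counted as a patient, and a bilateral share *b* of 10% to 40% of patients.

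**1. Is a combined estimate valid?** Each laterality group is randomised 1:1 from its own blocks, so each gives an unbiased arm contrast, and a weighted average of the two is also a randomised contrast. With equal allocation and common σ, inverse-variance weighting gives SE = σ√(2/150), the full-sample value.

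**2. Precision lost by stopping at the split.** A stratum holding a fraction *s* of patients has SE = σ√(2/(150*s*)), which is the full-sample SE divided by √*s*.

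**3. Power.** Suppose the full-sample estimate has 80% power. The true effect is then 1.96 + 0.84 = 2.80 standard errors, and power in a stratum is Φ(2.80√*s* − 1.96), with *s* = 1 − *b* (unilateral) or *b* (bilateral). At *b* = 10%:

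- unilateral: 2.80 × √0.90 − 1.96 = 0.70, power 76%
- bilateral: 2.80 × √0.10 − 1.96 = −1.07, power 14%

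**4. Detectable difference at 80% power.** This is 2.80 × √(2/*n*) in SD units. For the full sample, 2.80 × √(2/150) = 0.32 SD.

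| Bilateral share | Patients per arm, uni / bi | SE relative to full sample, uni / bi | Power, uni / bi | Detectable difference (SD), uni / bi |
|---|---|---|---|---|
| 10% | 135 / 15 | 1.05 / 3.16 | 76% / 14% | 0.34 / 1.02 |
| 20% | 120 / 30 | 1.12 / 2.24 | 71% / 24% | 0.36 / 0.72 |
| 30% | 105 / 45 | 1.20 / 1.83 | 65% / 34% | 0.39 / 0.59 |
| 40% | 90 / 60 | 1.29 / 1.58 | 58% / 43% | 0.42 / 0.51 |

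If a case is a hip, patients per arm are 150/(1 + *b*), i.e. 136 at 10% and 125 at 20%. The full-sample detectable difference becomes 0.34 or 0.35 SD. The power columns do not change, because they depend only on the share.

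**5. The scale matters for ions.** Suppose the raw arm difference is *D* with one bearing and 2*D* with two (an assumption). A single raw-scale estimate is then (1 − *b*)*D* + *b*·2*D* = (1 + *b*)*D*, or 1.1*D* to 1.4*D* over the range, which describes neither group. If a second bearing multiplies concentration by the same factor in both arms, the Magnum/Taper ratio is the same in both groups, and log concentration is the natural scale.

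**6. Can the common-effect assumption be tested?** The SE of the arm-by-laterality interaction is the full-sample SE divided by √(*b*(1 − *b*)). For an interaction as large as the 80%-power effect, power is Φ(2.80√(*b*(1 − *b*)) − 1.96), which is 13%, 20%, 25% and 28% at shares of 10%, 20%, 30% and 40%. A non-significant interaction would say little.

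**The case against.** The best defence is that separate analysis follows the design. Laterality is stratified at randomisation, a bilateral patient has two bearings feeding one blood and one urine measurement, and the split keeps different exposures apart. Each comparison is unbiased, nothing forbids combining them later, and doing so recovers full precision. All of that stands. It is a reason to keep the separate results. It does not supply the missing combined estimate or fix its scale in advance.

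Stronger readings are tempting, and the document does not support them:

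- *The split is an error and should be replaced by a pooled model.* A laterality term removes a difference in level between the groups, not a difference in arm effect. One estimate needs a common effect on some scale, and step 6 shows that the interaction test cannot establish this.
- *The split inflates the false-positive rate or multiplies the number of tests.* The plan states no significance level for these outcomes, no rule for claiming a result from one or both strata, and no testing visit by visit. The sections list sampling times; a repeated-measures model within each stratum would satisfy them equally well.
- *A primary test is weakened.* Ions and kidneys appear in a primary objective, but it is worded as an investigation. No hypothesis or sample size is attached, and ion release is listed as secondary.

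**Conclusion.** The point holds as a minor gap in completeness. The plan sets a randomised ion comparison between devices, and lists renal function as an endpoint of the same comparison, but specifies no estimate that uses all randomised patients.

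The cost is precision, not bias. Relative to 80% for a stratified full-sample estimate, power is about 76% to 58% in unilateral patients and 14% to 43% in bilateral patients. These figures rest on assumed bilateral shares of 10% to 40%, two-sided 0.05, and equal SD and equal standardised effect in the two groups. With a share near 10%, the unilateral analysis loses little and the weakness lies almost wholly in the bilateral result. The 80% is a reference level; the document makes no power claim for these outcomes.

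**What to change.** Keep the two sentences that require separate unilateral and bilateral results, and add to both sections one prespecified Magnum–Taper estimate in all randomised patients, stratified by laterality:

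- **Ions:** for cobalt and for chromium, analyse log concentration and report the arm ratio with its confidence interval, adjusted for the pre-operative value and laterality. Name the fluid, and the visit or average over visits, to which the estimate refers.
- **Renal function:** the same model on the renal measure, naming which one is used, since the section mentions both eGFR and creatinine clearance.
- **Interaction:** report the arm-by-laterality interaction as an estimate with its confidence interval, and do not treat a non-significant test as evidence that the strata agree.
- **Presentation:** show the unilateral, bilateral and combined results side by side.

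The cost is SAP wording and some analysis work; no extra patients, samples or visits are needed. The real downside is that the combined estimate assumes a similar arm effect in the two strata (for ions, a similar ratio). The trial has little power to check this, so the separate results must stay visible.
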